13.3 Unsolicited Adverse Events

If the reporting source is collected in the study, specify the following: The first-line analysis will use unsolicited adverse event data from all reporting sources combined. A second-line analysis will encompass the analysis of unsolicited adverse events by source (medical records, study specific worksheet).

All the unsolicited adverse events occurring during the study, judged either as probably related, possibly related, or not related to vaccination by the investigator, will be recorded. Safety data including medically-attended AE within 30 days after first occurrence, and RT-PCR confirmed ILI, adverse events leading to withdrawal, AESI, NOCD and SAE up to Day 366 will be captured. The original verbatim terms used by investigators to identify adverse events in the CRFs will be mapped to preferred terms using the MedDRA dictionary. The unsolicited adverse events will then be grouped by MedDRA preferred terms into frequency tables according to system organ class. Adverse events judged by the investigator as at least possibly related to study vaccine will be

summarized by vaccine group, according to system organ class and preferred term within system organ class. When an unsolicited adverse event occurs more than once for a subject, the maximal severity and strongest relationship to the vaccine group will be counted.

Only vaccine-emergent adverse events (see [section 8.7](#) for definition) will be analyzed, i.e., excluding those after a subject has given informed consent but before vaccination. The selection of unsolicited adverse events and the assignment to time intervals will be done by day of onset and not by days ongoing/persisting.

The summaries will be presented by period of onset and will include frequency distributions of the different adverse events:

- Onset between Day 1 and Day 22.
- Onset between Day 23 and Day 181.
- Onset between Day 182 and Day 366
- Onset between Day 1 and Day 366

A number of adverse events typically captured on diary cards will be reported as unsolicited adverse events. Unsolicited adverse events corresponding to local and systemic solicited events (for example, injection site pain, fatigue, etc.), which occur in the 7 days following vaccination, will be presented by treatment group.

The analysis of unsolicited adverse events comprises the following categories:

- Any unsolicited adverse event.
- Possibly or probably related unsolicited adverse events.
- Unsolicited adverse events leading to death.
- Serious adverse events.
- Possibly or probably related serious adverse event.
- Medically-attended AE within 30 days after first occurrence RT-PCR confirmed ILI
- Unsolicited adverse events leading to premature withdrawal from study.
- Unsolicited adverse events leading to new onset of chronic disease.
- Unsolicited adverse events of special interest.

Solicited adverse events continuing beyond Day 7 will be coded by MedDRA and will be reported into the respective unsolicited adverse events.

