2. OBJECTIVES

2.1 Primary Objective(s)

The primary and secondary efficacy objectives will be measured in all subjects in relation to cases of influenza occurring from 21 through 180 days after vaccination or through the end of influenza season, whichever is longer. In all cases, efficacy will be determined based on influenza cases caused by A (H1N1 and H3N2) and either B lineage.

Primary Efficacy Objective:

1. To demonstrate absolute vaccine efficacy of aQIV versus non-influenza comparator (Boostrix[®]) when administered as a single dose to prevent first occurrence RT-PCR-confirmed influenza, due to any strain of influenza regardless of antigenic match to the strains selected for the seasonal vaccine, in subjects \geq 65 years of age.

Primary Safety Objectives:

2. To evaluate the safety of aQIV through assessment for local and systemic solicited adverse events through Day 7 in a subset of subjects.
3. To evaluate the rates in each vaccine group of medically-attended adverse events within 30 days after the first occurrence RT-PCR confirmed ILI.
4. To evaluate the rates in each vaccine group of unsolicited adverse events for 21 days after vaccination and adverse events leading to withdrawal, serious adverse events (SAEs), adverse events of special interest (AESI), and new onset of chronic diseases (NOCD) for 365 days after vaccination.

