5.3.1 Follow-up Clinic Visit(s)

Safety follow-up clinic visits will be performed on Days 22 and 181.

During the follow-up clinic visit on Day 22, for subjects participating in the solicited safety subset, the Subject Diary will be reviewed and collected. No changes to the information recorded within the Subject Diary are permissible. For details on the Subject Diary see [Sections 3.4.2, Tools Used for Data Collection](#) and [5.2.1, Post-vaccination Procedures](#). The subject or legal guardian will be interviewed to determine if any unsolicited adverse events (including SAEs, ILIs, NOCDs, AEs leading to withdrawal and AESIs) occurred and if any concomitant medications or vaccines were taken/received during the time since the last clinic visit. This interview will follow a script which will facilitate the collection of relevant safety information. The healthcare professional reviewing these data will discuss the symptoms (if any) reported by the subject and will determine if any additional diagnoses and/or adverse events are present. All adverse events reported by the subject or legal guardian at this follow-up clinic visit must be recorded in the subject's source document and on an Adverse Events CRF, as specified in [Section 7.1, Safety Assessment](#), and not written on the script used for the interview.

During the follow-up clinic visit on Day 181, the subject will be interviewed to obtain information relating to a subset of unsolicited AEs (all SAEs, ILIs, NOCDs, AEs leading to withdrawal and AESIs) and use of medication to treat these.

During both follow-up clinic visits, the subject will be asked as to whether he or she was hospitalized or was evaluated at an emergency room or a physician's office for any illness since the site's last contact with the subject. If an SAE has been identified by the site staff during the interview which has not previously been reported by the subject, this SAE will be reported by the site within 24 hours to Seqirus or delegate. Any additional relevant medical history will be recorded as needed.

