During both follow-up clinic visits, an ILI assessment will be performed to determine if symptoms of ILI are present. Potential ILI symptoms will be documented in the subject's source records. If the onset of the ILI is 6 days or less before the visit, a NP swab should be collected from the subject for influenza testing and study staff will document the ILI on an Adverse Event and ILI CRF (see procedures described in [Section 5.4, Unscheduled Visits](#)).

During both follow-up clinic visits, a brief symptom-directed physical examination will be performed by a qualified health care practitioner according to symptoms the subject has reported. This physical examination will include an examination of organ systems that are considered relevant by the investigator based on review of the subject's reported adverse events, and concomitant medication use. This assessment may include measurement of vital signs (respiratory rate, blood pressure and heart rate), body temperature (preferably oral) and a check of general appearance. The physical assessment must be performed by the investigator or designee of the investigator, who is qualified to perform a physical assessment in accordance with their institutional policy. Measurement and recording of vital signs and body temperature may be conducted by a trained health care professional. Corresponding information is documented in the subject's source document and eCRF(s).

During the Day 22 follow-up clinic visit, approximately 10 ml of blood will be drawn from selected subjects participating in the immunogenicity season (see [Section 3.5, Collection of Clinical Specimens](#)).

The site should also schedule the next study activity, the safety call, with the subject or legal guardian. It is recommended for the site to also schedule in the remaining upcoming study activities whenever possible.

The subject or legal guardian will receive a written reminder of the next planned study activity. The subject or legal guardian will be reminded to contact the site immediately (or as soon as the subject is medically stable) if the subject has a medical condition that leads to a hospitalization, an emergency room visit, or a visit to/by a doctor, or is otherwise of concern.

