5.3.2 Safety Follow-up Calls

Safety follow-up calls will be performed on Days 15, 91 and 271.

Safety follow-up calls are calls made to the subject by a healthcare professional designated on the site log. These calls will follow a script which will facilitate the collection of relevant safety information. The subject or legal guardian will be interviewed according to the script. On Day 15, information will be collected regarding all unsolicited adverse events and concomitant medications or vaccinations associated with those events. Safety follow-up calls performed on Days 91 and 271 will collect information relating to a subset of unsolicited adverse events including SAEs, adverse events of special interest (AESIs), AEs leading to withdrawal, new onset of chronic disease (NOCD), ILI and concomitant medications or vaccinations associated with those events. All safety information described by the subject must be written down in a designated location within the source document and not written on the script used for the telephone call.

The subject will be asked as to whether he or she was hospitalized or was evaluated at an emergency room for any illness since the site's last contact with the subject. If an SAE has been identified by the site staff during the interview which has not previously been reported by the subject, this SAE will be reported by the site within 24 hours to Seqirus or delegate. Any additional relevant medical history will be reported to Seqirus or delegate and recorded as needed.

ILI assessments will be performed to determine if symptoms of ILI are present. If the subject reports during phone contact that a medical event has occurred with symptoms consistent with an ILI, the subject will be asked to visit the site for further evaluation and potential NP swab taking. An NP swab should be collected, for evaluation of the presence of influenza virus, preferably within 3, but up to 6, days after the first day of onset of ILI symptoms. See procedures described in [Section 5.4, Unscheduled Visits](#).

The subject or legal guardian will receive a reminder of the next planned study activity. The subject or legal guardian will be reminded to contact the site immediately (or as soon as the subject is medically stable) if the subject has a medical condition that leads to a hospitalization or an emergency room visit or to a visit to/by a doctor or is otherwise of concern.

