5.4.1 Subjects Meeting the Influenza-Like-Illness Criteria

Clinic Visit or Home Visit – Obtaining NP Swab

Subjects will be asked to come to the site for an unscheduled clinic visit when experiencing symptoms meeting the primary protocol-defined ILI criteria. In the exceptional case that a clinic visit is not feasible, a home visit may be considered. The visit should occur as soon as possible within 3, but up to 6, days after the first day of onset of ILI symptoms. During the visit the following procedures should be carried out:

- Assess ILI symptoms and assess associated medication. Document any anti-viral medication use from the first day of onset of ILI symptoms.
- Collect a NP swab for evaluation of the presence of influenza virus following the procedures for collecting, processing and shipping as described in the Lab Manual.

- Evaluate the subject's body temperature (preferably oral), heart rate, respiratory rate and blood pressure and perform a symptom-directed physical examination.
- Record the ILI, related information, medically-attended adverse events from ILI onset and associated concomitant medication in the source documents and in the eCRF (ILI-report and adverse events section).
- Schedule in next study activity

ILI Follow-up Safety Call

An ILI follow-up safety call will be performed at 30 (+7) days after primary protocol-defined ILI onset, amongst subjects who have had their NP swab obtained

During the visit the following procedures should be carried out:

- Assess ILI symptoms and associated medication, if any.
- Assess for medically-attended adverse event.
- Remind subject of next study activity.

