8.4.2.1.3 Analysis of Unsolicited Adverse Events

This analysis applies to all adverse events occurring during the study, judged either as probably related, possibly related, or not related to vaccination by the investigator, recorded in AE CRF, with a start date on or after the date of first vaccination. AE starting prior to the first vaccination will only be listed. The original verbatim terms used by investigators to identify adverse events in the CRFs will be mapped to preferred terms using the Medical Dictionary for Regulatory Activities (MedDRA) dictionary. The adverse events will then be grouped by MedDRA preferred terms into frequency tables according to system organ class (SOC).

All reported adverse events, as well as adverse events judged by the investigator as at least possibly related to study vaccine, will be summarized according to SOC and preferred term within SOC. These summaries will be presented by vaccination group and by interval of study observation. When an adverse event occurs more than once for a

subject, the maximal severity and strongest relationship to the vaccine group will be counted.

Separate summaries will be produced for the following categories:

- SAE;
- Adverse events that are possibly or probably related to vaccine;
- Medically attended adverse events that occur within 30 days following RT-PCR confirmed ILI
- AESI;
- NOCD;
- Adverse event leading to withdrawal;
- Adverse event resulting in death.

Data listings of all adverse events will be provided by subject. In addition, adverse events in the categories above will be provided as listed data.

For **handling of missing data** the entire study period will be divided into disjoint intervals based upon the time and event schedule in the protocol:

Solicited AEs: 30 min, 6h-Day 3, Day 4-Day 7, and one overall interval: 6h-Day 7.

Unsolicited AEs: [Day 1-22], [Day 23-181], [Day 182-366], and [Day 1-366].

No imputation of missing solicited or unsolicited AEs will be used. The percentage of subjects with missing solicited AE assessments (e.g. missing Patient Diary) and missing Safety Phone Call or safety assessment will be reported for each time period.

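### Any-AE summaries beyond Day 22 count RT-PCR-confirmed influenza a second time, as an adverse event, and so lean towards aQIV

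*SAP*

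**What the plan says.** **Collection.** Protocol 2.1 sets the objective for "unsolicited adverse events for 21 days after vaccination", with SAEs, AESIs, NOCDs and AEs leading to withdrawal followed for 365 days. The endpoints in Protocol 8.1.1.1 and SAP 2.1.4 keep the same split and treat medically-attended AEs after an ILI as a separate endpoint. At Day 181, Protocol 5.3.1 asks only for "a subset of unsolicited AEs (all SAEs, ILIs, NOCDs, AEs leading to withdrawal and AESIs". For the later calls, Protocol 5.3.2 says "Safety follow-up calls performed on Days 91 and 271 will collect information relating to a subset of unsolicited adverse events including SAEs", and its list also contains ILI. Protocol 5.5 has the same list for the final visit.

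**Recording.** Protocol 3.4.1 lists ILI, and medically-attended AEs within 30 days of ILI onset, among the adverse events. Where an ILI is found at a follow-up visit, "study staff will document the ILI on an Adverse Event and ILI CRF" (Protocol 5.3.1; likewise 5.5). For an ILI visit, Protocol 5.4.1 says "Record the ILI, related information, medically-attended adverse events from ILI onset and associated concomitant medication in the source documents and in the eCRF", naming both the ILI report and the adverse events section. Protocol 3.8 also sends post-ILI medically-attended AEs to the AE page.

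**Tabulation.** Protocol 8.4.2.1.3 opens with "This analysis applies to all adverse events occurring during the study" and takes its data from the AE CRF. It presents summaries by study interval and lists "Unsolicited AEs: [Day 1-22], [Day 23-181], [Day 182-366], and [Day 1-366" (the list closes there). SAP 8.2.1 and 13.3 repeat the four intervals. SAP 13.3 states "The summaries will be presented by period of onset and will include frequency distributions of the different adverse events", and the first category it analyses is any unsolicited AE. SAP 13.4 adds a combined summary of non-serious AEs for public posting. None of these sections excludes ILI, confirmed influenza or post-ILI events.

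**The concern.** The comparator gives no protection against influenza. Each confirmed case is an ILI, each ILI is to be entered as an AE, and every entered AE is to be tabulated up to Day 366. A working vaccine will therefore show fewer subjects with any AE after Day 22 even when the two vaccines are equally safe. A reader of those rows would see an apparent safety advantage that is the efficacy result again. The swabbed-ILI pathway, with its extra visit and 30-day call, can also add medically-attended AEs that would not be captured in a subject without an ILI.

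**Working it through.** **Inputs from the documents.** Attack rates of 3.5% (comparator) and 1.4% (aQIV), 4,860 evaluable subjects per arm and 238 events (Protocol 8.5, SAP 5).

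**Reproducing the plan's figure.** 4,860 × (0.035 + 0.014) = 238.1, which matches the stated 238.

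**Influenza cases entering as AEs.**
- Comparator: 4,860 × 0.035 = 170.1 subjects.
- aQIV: 4,860 × 0.014 = 68.0 subjects.
- Difference: 102.1 subjects, or 2.1 percentage points.

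These rates belong to the efficacy window, which starts 21 days after vaccination and ends at 180 days or season end, whichever is later. Nearly all such cases have onset after Day 22. Most would fall in the Day 23-181 table, any between Day 181 and season end in the Day 182-366 table, and all of them in the Day 1-366 table.

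**Dependence on true efficacy.** The difference is 3.5% × VE: 0.7 points at VE 20%, 1.4 at 40% and 2.1 at 60%.

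**Effect on the any-AE row.** Let b be the proportion with any other recorded AE in the interval. It is assumed equal by arm and independent of influenza. The documents give no value for b, so a range is shown.

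- Comparator risk = 1 − (1 − b)(1 − 0.035)
- aQIV risk = 1 − (1 − b)(1 − 0.014)
- Difference = (1 − b) × 2.1 points

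| Assumed b | Comparator | aQIV | Difference (points) | Risk ratio |
|---|---|---|---|---|
| 5% | 8.3% | 6.3% | 2.0 | 0.76 |
| 10% | 13.2% | 11.3% | 1.9 | 0.86 |
| 20% | 22.8% | 21.1% | 1.7 | 0.93 |
| 40% | 42.1% | 40.8% | 1.3 | 0.97 |

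**Where b is likely to lie.** It must include non-influenza ILIs, because they go on the AE CRF too and the case definition is broad (one respiratory plus one systemic symptom). For Day 1-366 it must also include every unsolicited AE from Day 1-22. Both raise b and move the ratio towards 1. The absolute gap shrinks only by the factor (1 − b). Post-ILI medically-attended AEs are not in this calculation.

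**The case against.** The strongest reply is that the prespecified endpoints already make the right split, and this stands. Protocol 8.1.1.1 and SAP 2.1.4 limit any unsolicited AE to Day 1-22 and give the year-long categories and the post-ILI events their own endpoints. SAP 13.3 also gives them their own table categories, but those come in addition to the any-AE category and take nothing out of it.

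Three stronger readings are tempting, and the documents do not support them.
- *That non-serious AEs after Day 22 arise mainly from ILIs.* No ILI rate or background AE rate is given, and non-serious NOCDs, AESIs and withdrawal AEs also enter.
- *That ascertainment is unequal by arm by design.* The collection rules are the same in both arms and observer-blind (Protocol 3.3), weekly surveillance covers everyone (5.3.3), and the 30-day call follows any swabbed ILI whatever the PCR result (5.4.1). Only the influenza-positive share is expected to differ.
- *That these tables decide the safety conclusion or hide a true excess on aQIV.* Protocol 8.2 does ask for an acceptable safety profile, but 8.2.1.1 sets no safety success criterion and no test of AE rates is planned. Tables by preferred term would show influenza as its own row and an excess elsewhere in its own row. Even so, overall and system-organ-class subject counts cannot be corrected from those rows, because one subject can appear in several.

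It can also be said that the table list is held outside the SAP, and that SAP 13.3 lists intervals and categories separately without expressly crossing them. That is fair, but nothing limits the any-AE category to Day 1-22, and Protocol 8.4.2.1.3 presents the all-AE summaries by interval.

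Finally, Protocol 7.1 and 7.1.2 and SAP 13.3 can be read as recording every AE to Day 366. That conflicts with Protocol 5.3.1 and 5.3.2. Even on that reading influenza is still counted as an AE, against a higher background.

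**Conclusion.** The point holds, within limits. As written, the plan produces any-AE summaries for Day 23-181, Day 182-366 and Day 1-366 in which confirmed influenza is counted again as an AE. At the planned rates this adds about 170 comparator and 68 aQIV subjects, or 2.1 points before overlap with other AEs. The resulting risk ratio depends on a background rate that the documents do not give: about 0.76 to 0.97 for backgrounds of 5% to 40%, with non-influenza ILIs and Day 1-22 AEs pushing it towards 1. The calculation rests on the planned 60% efficacy, equal backgrounds by arm, and each confirmed case being entered on the AE CRF.

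The affected outputs are these descriptive any-AE summaries and the combined non-serious posting table in SAP 13.4. The Day 1-22 endpoint is largely unaffected. The separate SAE, AESI, NOCD and withdrawal tables are affected only where influenza itself leads to such an event. This is a cheap improvement to make before unblinding; it does not threaten the primary safety endpoints.

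**What to change.** - In Protocol 8.4.2.1.3 and SAP 8.2.1 and 13.3, limit any and related unsolicited AEs to Day 1-22, in line with the trial's own endpoints.
- For Day 23-181, 182-366 and 1-366, tabulate only SAEs, AESIs, NOCDs, AEs leading to withdrawal and deaths.
- Show ILIs and post-ILI medically-attended AEs in their own table.
- Show SAEs, and the combined summary in SAP 13.4, with and without RT-PCR-confirmed influenza and post-ILI events.
- Reconcile Protocol 7.1 and 7.1.2 and SAP 13.3 (all AEs recorded) with Protocol 5.3.1 and 5.3.2 (a subset only after Day 22).

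The cost is wording, changed shells and a few extra tables, with no new data. There would be no overall any-AE figure to Day 366, which collecting only a subset after Day 22 cannot properly support. Making the change before unblinding avoids the appearance of removing influenza after the results are known.

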13.4 Combined Solicited and Unsolicited Adverse Events

A summary of number of subjects with all combined solicited (regardless of their duration) and unsolicited adverse events will be provided, regardless of their duration and recurrence. Solicited adverse events will be coded by MedDRA. For clintrial.gov and EudraCT posting purposes, a summary of combined solicited and unsolicited non-serious adverse events will be produced by System Organ Class and according to occurrence of each event. A further differentiation of combined adverse events according to seriousness, severity, or relationship is not performed.

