Twenty percent of subjects (every 5th subject enrolled from each treatment arm) will be designated during randomization, across all sites and countries, for Solicited Safety Set, see [section 7.5](#).

For further details please refer to Section 5.1.4 of the protocol.

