5. SAMPLE SIZE AND POWER CONSIDERATIONS

Efficacy objectives:

Sample size and power consideration for the aQIV efficacy objective is based on criteria for demonstrating efficacy in placebo controlled studies provided in CBER guidance, specifically that the study should be powered to assess the lower bound of the two-sided 95% CI of vaccine effectiveness, anticipated to be substantially above zero. This study is planned using a group sequential design. The power of Cox Regression which is planned to be used for analysis is dependent on the overall number of influenza cases, so the sample sizes on number of subjects described in this section is provided more for operational reasons. Additional information on the planning of number of subjects that may need to be enrolled if it is decided to continue enrolment after interim analyses is described in [Section 8.6](#).

For the primary efficacy objective: with 1-sided alpha of 2.5% and assuming an attack rate of influenza of 3.5% among subjects enrolled in the non-influenza comparator group and 1.4% among the aQIV group, i.e. 60% assumed vaccine efficacy for aQIV, 238 events (i.e. 4,860 subjects per group under the assumed ERs) are needed with 86.5% power to show the absolute efficacy of aQIV versus non-influenza comparator, in preventing first occurrence RT-PCR-confirmed influenza A and/or B, due to any strain of influenza regardless of antigenic match to the strains in aQIV, in subjects ≥ 65 years of age, using a margin of 40% for lower bound of the CI for absolute vaccine efficacy.

For the first secondary efficacy objective: with a group vaccine efficacy of 65% but expecting conservatively reduced event rates of influenza cases due to matched strains of 2.5% among subjects in the non-influenza comparator group and 0.9% among the aQIV group then 144 events has estimated power approximately 88.5% to show the absolute efficacy of aQIV versus non-influenza comparator, using a margin of 40% for lower bound of the CI.

Assuming a drop-out rate of 10%, approximately 10,692 subjects ≥ 65 years, 5,346 per vaccine group will be randomized to receive either aQIV or non-influenza comparator (Boostrix®) in a 1:1 allocation ratio, stratifying by age (≥ 65 to 74 and ≥ 75 years of age), study site and by low vs high risk of influenza complications (score < 50 vs ≥ 50).

Immunogenicity objective:

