7.5 Safety Set

Solicited Safety Set

All designated subjects (i.e., a sample of 1053 subject from each treatment arm) in the Exposed Set, with solicited safety assessments beyond 30 minutes (e.g., use—or lack of use—of analgesics/antipyretics).

Unsolicited Safety Set

All subjects in the Exposed Set with unsolicited adverse event data.

A record of safety assessment performed at a specific time point, with confirmation of no AE, is considered as adverse event data hence subject is to be included.

Overall Safety Set

All subjects who are in the solicited safety set and/or in the unsolicited safety set.

Subjects providing only 30 minute post-vaccination safety data will be reported separately in a 30 minute post-vaccination safety analysis and excluded from all other safety analysis.

In case of vaccination error, subjects will be analyzed as “treated” (i.e., according to the vaccine a subject receives, rather than the vaccine to which the subject is randomized).

If a subject received the correct study vaccine (dose, batch) but from another ongoing study at the site then the subject’s safety data should be included in the safety analyses.

In case a subject is randomized in the wrong stratum:

- Subject will be reassigned to the correct stratum for solicited and unsolicited safety analyses.

If a subject is unblinded during the study, he/she will be included in all the safety analyses.

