13.1.1 Safety Completeness Analysis

Solicited adverse events

The safety completeness analysis on solicited adverse events aims to identify subjects who completed diary cards, irrespective of severity. The analysis will show the number of subjects with valid data by solicited adverse event and time point. Valid data in the context of the safety completeness analysis are all data entered in the diary card (including implausible values) except “Not done/unknown”.

Four summaries will be produced:

1. The frequencies of subjects who provide diary cards by vaccine group.
2. For each solicited adverse event, the frequencies of subjects with valid data will be presented by vaccine group and timepoint: 30 min, 6h –Day 3, Day 4-7, 6h - Day 7, Day 1 – 7 (with/without 30 mins).
3. For each type of solicited adverse event (local, systemic) and indicators of solicited adverse events, such as analgesic use, the frequencies of subjects with valid data by vaccine group, aggregated over time points: 30 min, 6h –Day 3, Day 4-7, 6h - Day 7, Day 1 – 7 (with/without 30 mins).
4. For each solicited adverse event, the frequencies of subjects with valid data by vaccine group, aggregated over time points: 30 min, 6h –Day 3, Day 4-7, 6h - Day 7, Day 1 – 7 (with/without 30 mins).
5. For the corresponding percentages, the denominator will be the respective numbers of exposed subjects, i.e., subjects who received a vaccination and were still in-study for that time point or time interval, irrespective of whether a diary card was present or not.

All analyses will be based on the ‘as treated’ Solicited Safety Set.

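### SAP 13.1.1 measures diary completeness on a set that already requires diary data, against its own denominator rule; secondarily, SAP 13.4 merges diary and unsolicited events for registry posting without naming a denominator

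*SAP*

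**What the plan says.** **Who gets a diary.** SAP 4.1: "Twenty percent of subjects (every 5th subject enrolled from each treatment arm) will be designated during randomization" for the solicited subset. Protocol 3.4.2 makes the diary the only source for solicited local and systemic events after the first 30 minutes. SAP section 3, by contrast, still says that every subject receives a Subject Diary.

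**Analysis sets (SAP 7.5).**
- The Solicited Safety Set is defined as: "All designated subjects (i.e., a sample of 1053 subject from each treatment arm) in the Exposed Set, with solicited safety assessments beyond 30 minutes".
- Unsolicited Safety Set: "All subjects in the Exposed Set with unsolicited adverse event data".
- Overall Safety Set: "All subjects who are in the solicited safety set and/or in the unsolicited safety set".

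**Completeness (SAP 13.1.1).** The first listed summary is the frequency of subjects who provide diary cards. The others count valid data by event, event type and time point. The percentage denominator is vaccinated subjects still in the study, "irrespective of whether a diary card was present or not". The closing sentence of the section bases all of these analyses on the as-treated Solicited Safety Set. SAP 8.2.1 separately promises the percentage with missing solicited assessments for each period, with no denominator.

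**Combined table (SAP 13.4).** "A summary of number of subjects with all combined solicited (regardless of their duration) and unsolicited adverse events will be provided". A combined non-serious summary by system organ class and event is also planned for two public registries. No analysis set, denominator or percentage is given.

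**The concern.** A completeness analysis exists to show how much diary information was lost. If the set it runs on is defined by having that information, subjects who returned nothing are removed before counting, and the table cannot show the loss it is meant to measure. Solicited events by diary are one of the primary safety objectives, so a reader of the report needs an honest return rate to judge them.

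The combined table raises a related denominator question. One row, such as injection-site pain, could mix prompted daily diary entries from about a fifth of subjects with spontaneous reports from the rest. SAP 13.3 expects diary-type events to be reported as unsolicited events too. SAP 13.2 guards its own tables by dropping subjects without plausible data from the denominator, for the stated purpose of avoiding bias towards zero. SAP 13.4 carries no such safeguard, and its output is meant for public posting.

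**Working it through.** **Inputs.** 1,053 designated per arm (SAP 7.5). 1,000 evaluable per arm in the Solicited Safety Set, 4,860 evaluable per arm overall, and missing diary data of up to 5% (SAP section 5). For the planned size: "5,346 per vaccine group will be randomized to receive either aQIV or non-influenza comparator" (SAP section 5).

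**The plan's own figures reproduce.**
- 1,000 / (1 − 0.05) = 1,052.6, rounded up to 1,053.
- Chance of at least one event at rate 0.002 in 1,000 subjects: 1 − 0.998^1000 = 0.865, against the stated 86%.

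**Completeness under three readings of SAP 13.1.1**, with 53 of 1,053 designated subjects returning no diary data (the planned maximum):

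| Denominator | Calculation | Diary return |
|---|---|---|
| Solicited Safety Set (closing sentence of 13.1.1) | 1,000 / 1,000 | 100% by construction |
| All exposed subjects, taken literally | 1,000 / 5,346 | 18.7% |
| Exposed subjects designated for the subset | 1,000 / 1,053 | 95.0% |

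If 10% or 20% returned nothing (assumed), the third row would read 948/1,053 = 90.0% or 842/1,053 = 80.0%. The first row would not move. The literal second row is no better, because it counts subjects who were never given a diary.

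**Dilution in SAP 13.4, if the Overall Safety Set were the denominator.** Let f be the share of subjects with a diary, and r the rate at which non-diary subjects report such events, relative to the diary rate. Then fold dilution = 1 / [f + (1 − f)r].

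- f = 1,053 / 5,346 = 0.197, so at r = 0 the ceiling is 5.08-fold.
- f = 1,000 / 4,860 = 0.206, so at r = 0 the ceiling is 4.86-fold.

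The documents do not give r, so it is varied. An illustrative diary rate of 30% is also an assumption. With f = 0.197:

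| r (assumed) | f + (1 − f)r | Fold | 30% would appear as |
|---|---|---|---|
| 0 | 0.197 | 5.1 | 5.9% |
| 0.10 | 0.277 | 3.6 | 8.3% |
| 0.25 | 0.398 | 2.5 | 11.9% |
| 0.50 | 0.598 | 1.7 | 18.0% |

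If r is the same in both arms, both arms' rates are multiplied by the same factor. Absolute rates and differences shrink, and the between-arm ratio does not change.

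**The case against.** *Completeness.* The denominator sentence in 13.1.1 states the right intention, SAP 8.2.1 promises the missing-diary percentage independently, and SAP 9.1 reports how many subjects are in each analysis set. Entry to the Solicited Safety Set needs only some assessment beyond 30 minutes, so partial diaries are in the set and their gaps appear in the by-event and by-time-point summaries. This stands in part. A reader might infer that missing diaries vanish from the report altogether, and the documents do not support that. But 8.2.1 names no denominator, and 9.1 does not say that the designated number will be shown beside the set size. Neither settles the conflict over wholly missing diaries.

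*Combined table.* A reader might infer that posted reactogenicity rates will be understated five-fold. The documents do not say so. SAP 13.4 speaks of numbers of subjects and fixes no rate. Nor is the Overall Safety Set the only candidate: subjects in the Solicited Safety Set also give unsolicited data, so the combined table could be run there without dilution. The denominator may be set in the table of contents or mock-up catalogue cited in SAP sections 17 and 18, which are not part of these documents. The ceiling also needs complete silence from non-diary subjects, although all subjects are asked about adverse events at Days 15 and 22. All of this stands. It reduces the point to an unspecified denominator and does not remove it.

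**Conclusion.** The contradiction in SAP 13.1.1 is established from the text alone. Following its closing sentence, diary return is about 100% whatever happens, where the planning assumption allows 95.0%. The effect is confined to wholly missing diaries; item-level and time-point gaps remain visible.

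The SAP 13.4 point is secondary and conditional. Dilution arises only if the Overall Safety Set, or all exposed subjects, is used as the denominator. Its size then depends on r, which the documents do not give: about 5-fold is a ceiling, and 3.6- to 1.7-fold corresponds to assumed r of 0.10 to 0.50. The reactogenicity tables in SAP 13.2 and the primary safety endpoint, which is defined in the solicited subset, are not affected.

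**What to change.** 1. **SAP 13.1.1:** replace the closing sentence so that completeness is based on all exposed subjects designated for the solicited subset, analysed as treated, with or without a diary. Retain the still-in-study condition for each interval.
2. **SAP 8.2.1:** use the same denominator for the percentage with missing solicited assessments.
3. **SAP 13.4:** either produce the combined table in the Solicited Safety Set, or post solicited terms over the Solicited Safety Set and unsolicited terms over the Unsolicited Safety Set as separate rows.
4. **SAP section 3:** reconcile the statement that all subjects receive a diary with SAP 4.1 and 7.5.

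The cost is SAP wording and table shells. No new data are needed. The designation is made at randomization, so the designated denominator should already be on record.
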